Secondary Objectives:	
1. To identify imaging biomarkers that are associated with the probability of any post-treatment improvement of FEV1 of 5% or more2. To identify imaging biomarkers that are associated with the probability of any post-treatment reduction in maintenance OCS use							
Exploratory Objectives:	
1. To identify imaging biomarkers that are associated with the probability of any reduction in pre-treatment baseline hospitalizations for asthma2. To identify imaging biomarkers that are associated with the probability of any post-treatment improvement in ACT score3. To identify imaging biomarkers that are associated with the probability of any subjective post-treatment reduction in symptoms described clinically							
Endpoints:	Primary Endpoint:	Determine the cutoff value in chest wall muscle size/quality that optimally classifies patients that had and did not have any reduction in pre-treatment baseline exacerbation frequency (binary). Alternative (continuous): determine the strength of the linear/non-linear relationship						

	between continuous chest wall muscle size/quality and continuous change in exacerbation frequency
Secondary Endpoints:	
 1. Determine individual and combinations of body composition measures (phenotypes) associated with a 5% or greater improvement in FEV1 when compared to baseline FEV1 2. Determine individual and combinations of body composition measures associated with any reduction in maintenance OCS use when compared to baseline OCS use
Exploratory Endpoints:	
These endpoints may be limited in scope of analysis by the sample size within each of the outcome groups.
 
 1. Determine individual and combinations of body composition measures associated with any reduction in hospitalizations when compared to baseline hospitalizations 2. Determine individual and combinations of body composition measures associated with any improvement in ACT score when compared to baseline ACT score 3. Determine individual and combinations of body composition measures associated with any subjective improvement of symptoms when compared to baseline symptoms

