2.2 BACKGROUND

Innovation—Expanding on the Role of Body Composition

Nearly all research in severe asthma patients, including phase 3 trials for the current biologic therapies, has used BMI as a surrogate of body composition. Even when CT imaging has been used to better characterize body composition through relatively simplistic maneuvers such as calculation of total visceral and subcutaneous fat mass there have been no clinically usable predictive results from such analyses and no information about the role of the chest wall^{3,4}. Morphomics is a combination of high-throughput image analysis and deep learning techniques that enable the segmentation of tissues to precise detail, enabling the characterization of body composition to an unparalleled degree^{5,6}. Furthermore, the University of Michigan analytic morphomics group has an existing relational database of over 120,000 subjects that enables the generation of thousands of precise measurements, such as fat distribution, bone mineral density, and muscle density and size, and that can serve as a reference population for our asthma cohorts. This will allow for the accurate identification of extensive body composition patterns that differ from the norm utilizing an imaging population database on a scale that has never been done before.

Analytic morphomics provides actionable quantification of patient heterogeneity for precision medicine.

Precision medical intervention requires granular, precise, and actionable data at the time of treatment. Supported by rapid advances in new high-throughput technologies, “omics” data provide a unique opportunity to better understand pathophysiology and to translate research findings to clinical practice. These data enable clinicians to shift from traditional one-size-fits-all

treatment toward more targeted and precisely individualized therapies. Over the past decade, research at the University of Michigan has demonstrated that **morphomics** is the “omics” data most proximate to a patient’s ultimate health outcome (**Figure 2**).

[figure not shown]
[figure not shown]

Figure 2: Morphomics is the "omics" most proximate to treatment

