6.3 IDENTIFICATION OF BIOMARKERS FOR OUTCOMES

To incorporate high-dimensional morphomic parameters to better stratify patients in regard to their probability of complete response, we will leverage the regularization technique in machine learning to select important variables and develop risk predictive models. To be more specific, elastic net regularization will be utilized to address the high dimensional nature of data derived with analytic morphomics. Elastic net consists of a linear combination of L1 (lasso) and L2 (ridge) penalty to address over-fitting and co-linearity, respectively. In addition, to capture potential non-linear effects among variables, we will also apply random forest and gradient boosting, two highly utilized ensemble tree-based methods. Sample splitting will be used to assess model performance. We will evaluate the accuracy of developed predictive models by various performance measures, including Harrell's Concordance index, integrated cumulative area under the curve, and integrated brier score. The final developed predictive model will be evaluated on an independent dataset from the University of Calgary.

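### Section 6.3 names CT biomarkers by elastic net selection but checks only whole-model accuracy, so the list of named measures has no error control

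*Combined protocol and SAP*

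**What the plan says.** The objectives (section 1.1 and the table in section 3) are all to identify imaging biomarkers: one primary, two secondary and three exploratory. The secondary and exploratory endpoints in the synopsis ask for single measures as well as combinations; the first reads "Determine individual and combinations of body composition measures (phenotypes) associated with a 5% or greater improvement in FEV1". The primary endpoint in the synopsis is narrower. It concerns a cutoff in chest wall muscle size or quality or, alternatively, the relationship of that measure to the change in exacerbations.

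Section 2.2 says that the morphomics database "enables the generation of thousands of precise measurements". The number of measures to be analysed is not stated.

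Section 6.3 covers selection and modelling in one step: "we will leverage the regularization technique in machine learning to select important variables and develop risk predictive models". The tool is named: "elastic net regularization will be utilized to address the high dimensional nature of data derived with analytic morphomics". It adds: "we will also apply random forest and gradient boosting, two highly utilized ensemble tree-based methods". Success is judged on the model: "We will evaluate the accuracy of developed predictive models by various performance measures", and "Sample splitting will be used to assess model performance". The final model is then evaluated in the Calgary data.

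Two other places describe Calgary at the level of variables. The study description in the synopsis says the biomarkers will be tested there for validity, and the schema in section 1.2 lists applying the derived predictive variables to the Calgary data. Neither they nor section 6.3 gives a test, a direction or a correction for a single measure.

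**The concern.** Naming a biomarker and building a predictor are different tasks. A penalty chosen for predictive accuracy tends to keep many irrelevant variables, because weakly weighted noise costs little accuracy. The selected set carries no error rate for the statement that a given measure is associated with the outcome. Sample splitting and the accuracy measures do not supply one. Nor does evaluation of the final model in Calgary: a model can validate there on a few true measures while most of those it names are noise.

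The plan also gives no mixing weight, no rule for choosing the penalty, and no rule for reconciling the elastic net's list with what random forest and gradient boosting rank highly.

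At stake is the list itself. Section 3 presents the biomarkers as information for clinicians considering biologic initiation, and section 2.2 as a means of enriching future studies. A reader of the results could not tell which named measures to rely on.

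**Working it through.** **No figure to reproduce.** The documents state no alpha, power, false discovery rate or expected number of false selections.

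**Inputs from the documents.** About 300 Michigan and 200 Calgary patients (section 4.1); about 15% non-responders (section 4.1). Hence 300 × 0.15 = 45 non-responders in Michigan and 200 × 0.15 = 30 in Calgary, if 15% applies to the endpoint and the site. The follow-up exclusion in section 5.2 and sample splitting would lower the Michigan count.

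**Assumptions, not in the documents.** Logistic elastic net, mixing weight 0.5, penalty by 5-fold cross-validated deviance; two penalty rules, the minimum (Min) and one-standard-error (1SE); measures in blocks of 10 with within-block correlation 0.5 unless noted; 60 runs per scenario.

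**With true signals.** Mean share of named measures that are false, among runs that named any. Figures in brackets credit any measure in the same block as a true one.

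| Scenario | Min | 1SE |
|---|---|---|
| 1000 measures, 5 true, OR 1.5 | 81% (64%) | 63% (45%) |
| 1000, 5 true, OR 2 | 82% (66%) | 62% (41%) |
| 1000, 10 true, OR 1.5 | 80% (60%) | 65% (41%) |
| 200, 5 true, OR 2 | 80% (50%) | 63% (27%) |
| 2000, 5 true, OR 2 | 85% (71%) | 60% (45%) |
| 1000 independent measures, 5 true, OR 2 | 84% (81%) | 59% (57%) |
| 1000, 5 true, OR 2, event rate 50% | 88% (74%) | 69% (50%) |

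In the second row at Min, 32.7 measures were named on average: 4.0 of the 5 true ones and 28.6 others. The bracketed 57% comes from independent measures, where there are no real proxies; with correlated measures the 1SE range is 27–50%.

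A separate simulation (300 measures, blocks of 10 correlated at 0.6, three true at OR 1.6, minimum rule, 40 runs) named 14.6 on average. Of these, 10.0 lay outside any true block, a mean false share of 60% with proxies credited.

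**With no signal.** Share of analyses naming at least one measure, per endpoint:
- Minimum rule: 35% (1000 measures, 60 runs), 33% (500, 40 runs), 43% (300, 60 runs).
- One-standard-error rule: 7% (1000 measures, 60 runs).
- Simulation error on the 35%: √(0.35 × 0.65 / 60) = 0.06, or 6 points.

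**A strict selection gate.** Stability selection on the same elastic net used 1000 measures, 40 half-samples, a frequency threshold of 0.75, and at most √((2 × 0.75 − 1) × 1000 × 1) ≈ 22 measures per half-sample, over 15 runs. With no signal, mean false selections were 0.07, against 6.8 at the cross-validation minimum. With 5 true measures at OR 2 they were 0.0, against 28.6, but only 1.4 of the 5 true measures were found, against 4.0.

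**Power of a single-measure test in Calgary.** For OR 1.6 per SD, ln 1.6 = 0.470. SE ≈ 1/√(200 × 0.15 × 0.85) = 1/√25.5 ≈ 0.20, and 0.470/0.20 = 2.35.
- At two-sided 0.05: Φ(2.35 − 1.96) = Φ(0.39) ≈ 65%.
- At 0.005 (Holm's first step with ten named measures, 0.05/10): Φ(2.35 − 2.81) = Φ(−0.46) ≈ 32%, about one third.

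**The case against.** **Calgary is a real external check.** A reader of section 6.3 alone might infer that the biomarkers themselves are never tested in Calgary. The documents do not support that: the synopsis and the schema both announce a step at the level of biomarkers or variables. What stands is that the step is announced without a test, a direction or a correction.

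**The tuning rule is not stated.** It is tempting to say that the net is tuned purely for prediction and that most named measures will be noise. The predictive purpose and accuracy measures point that way, but no rule is given, and the result depends on it. Under the one-standard-error rule with correlated proxies credited, the false share is about half or less wherever measures are correlated. This limits the size of the concern; the missing rule remains part of the gap.

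**Multiplying over six endpoints.** A reader might take the 35% no-signal rate and compute 1 − 0.65⁶ = 92% for at least one false biomarker in the study. That does not hold. Section 4.1 counts a hospitalization as an exacerbation, so the endpoints are not independent. The figure counts Michigan selections before any Calgary check. Under the one-standard-error rule the same arithmetic gives 1 − 0.93⁶ = 35%.

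**The candidate set may be small.** The synopsis limits the primary endpoint to chest wall muscle, and the thousands of measures in section 2.2 describe what the database can generate, not what will be analysed. Both points are right. However, section 6.3 does not carry the restriction over, it would not cover the secondary endpoints, and the false share of exact measures was still 80% (Min) and 63% (1SE) with only 200 candidates.

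**Discovery work tolerates false leads.** This is fair for the three exploratory endpoints, and it argues against making strict stability selection the sole criterion, since that loses true measures.

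**Conclusion.** The concern holds. Followed as written, section 6.3 yields a list of named measures with no error control, for aims that consist of naming measures. In all seven signal scenarios, and under both penalty rules, most of the exact measures named were false: 80–88% at the minimum and 59–69% under the one-standard-error rule. Crediting correlated proxies under the latter rule lowers this to 27–57%, so the statement that most are noise is firm for exact measures but not for the regions or tissues they stand for. With no signal, the per-endpoint chance of naming something ranges from about 7% to 33–43%, depending mainly on a rule that the plan leaves open.

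These sizes rest on assumed numbers of measures, correlations, effect sizes and mixing weight, and on 40 to 60 runs per scenario. The direction does not depend on any one of these choices. The concern weighs most on the two secondary endpoints, and on the primary if 6.3 is meant to range beyond chest wall muscle. It should be corrected before the outcome analysis; it does not undermine the predictive modelling.

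**What to change.** 1. Keep the elastic net for prediction, and state the candidate measures, the mixing weight and the penalty rule.
2. For each endpoint, report every measure's selection frequency over repeated half-samples, beside a reference obtained by permuting the outcome. Use these frequencies to describe stability, not as the sole gate.
3. Fix the named list for each endpoint on Michigan data. Test each named measure singly in Calgary, and call it a validated biomarker only if it is associated in the same direction after Benjamini-Hochberg or Holm correction over the named measures for that endpoint. This specifies the step that the synopsis already announces.
4. Label all other selected measures hypothesis-generating.
5. For the primary endpoint, reconcile section 6.3 with the chest wall muscle definition in the synopsis.

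The cost is computing time, SAP wording and fewer confirmed measures; no new data are needed. With about 65% power at 0.05 and about one third at 0.005 for OR 1.6 per SD, many true associations will not be confirmed. The report must therefore say that failure to confirm in Calgary is not evidence of no association.

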3 OBJECTIVES AND ENDPOINTS

OBJECTIVES	ENDPOINTS	JUSTIFICATION FOR ENDPOINTS
Primary		
To identify imaging biomarkers that are associated with the probability of any reduction in pre-treatment baseline exacerbation frequency in a severe asthma population on biologics	Any reduction in exacerbations when compared to baseline exacerbations	Reduction in exacerbations is the primary clinical endpoint used in phase III trials to get many of the biologics used in asthma approved. Finding imaging biomarkers that associate with and possibly predict which patients will not have a reduction in exacerbations would be critical information for clinicians considering biologic initiation.
Secondary		
To identify imaging biomarkers that are associated with the probability of any post-treatment improvement of FEV1 of 5% or more	5% or greater improvement in FEV1 when compared to baseline FEV1	FEV1 is an important measure of lung function for patients with asthma, and any imaging biomarkers that predict a failure to improve this measure would be clinically useful.
To identify imaging biomarkers that are associated with the probability of any post-treatment reduction in maintenance OCS use	Any reduction in maintenance OCS use when compared to baseline OCS use	OCS are associated with multiple comorbidities, especially in the asthma population. Multiple phase III studies are currently underway to study maintenance OCS reduction in asthma due to this clinical concern and is a common reason for initiating biologics. Any imaging biomarkers that predict a failure to wean OCS after biologic initiation would be clinically useful.
Exploratory		
To identify imaging biomarkers that are associated with the probability of any reduction in pre-treatment baseline hospitalizations for asthma	Any reduction in hospitalizations when compared to baseline hospitalizations	Hospitalizations represent the most severe form of exacerbation and being able to find imaging biomarkers that associate with no improvement in hospitalizations would be clinically significant.
To identify imaging biomarkers that are associated with the probability of any post-treatment improvement in ACT score	Any improvement in ACT score when compared to baseline ACT score	Failure to improve symptoms after biologic initiation is a clinically frustrating scenario and finding imaging biomarkers that can predict this would be important for biologic initiation.

OBJECTIVES	ENDPOINTS	JUSTIFICATION FOR ENDPOINTS

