
For the purposes of our analysis, we will define baseline measurements as the average of all data obtained in the year prior to biologic initiation or, if only one clinical encounter (defined as an office or emergency room visit) is available in this time period, then the average of the 2 clinical encounters immediately prior to biologic initiation will be used with the time frame noted in the database. In order to assess our primary and secondary outcomes we will use the average of all data from 4 to 18 months after biologic initiation or, if only one clinical encounter is available in this time period, the average of the 2 clinical encounters closest to, but not before 4 months after, biologic initiation. If a second biologic is introduced or the initial biologic choice is

changed, we will use all clinical data prior to the change, even if it is before 4 months of use, then follow the above steps to collect new outcome data on the new drug (see **Figure 4**).

[figure not shown]

Figure 4. Baseline and Response Clinical Data Plan.

Since our interest is primarily in finding the ~15% of patients who do not respond to biologics, we have chosen to include partial and complete responders together in our endpoints in order to isolate the non-responder population. Table 1 below will represent the dichotomization of responders and non-responders for each endpoint using the baseline and post-biologic data as detailed above. An exacerbation will be defined as any hospitalization, urgent care, emergency room, or unscheduled office visit for asthma or a breathing-related complaint or a temporary increase of OCS or ICS dosing for 3 or more days with the intent of the increase to treat acute symptoms. For clinician response, clinical encounter notes will be read and interpreted by 2 independent physicians and graded as detailed in the table. Upon completion of all data abstraction the patient will be de-identified as described in data handling below.

	Responder	Non-responder
Exacerbations	Any decrease from baseline	No change from baseline
Hospitalizations	Any decrease from baseline	No change from baseline
Maintenance oral corticosteroid (OCS) use	Any decrease from baseline	No change from baseline

Change in FEV1	$\geq 5\%$ improvement from baseline	<5% improvement from baseline
ACT score	≥ 1 -point improvement from baseline	No change from baseline
Clinician impression of response to therapy	Any improvement in symptoms from baseline	No change from baseline

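### No outcome analysis specifies a baseline term although every responder label is a change from baseline, so a CT measure that tracks baseline severity can be credited as a response biomarker

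*Combined protocol and SAP*

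**What the plan says.** **Labels.** Section 4.1 states "we will define baseline measurements as the average of all data obtained in the year prior to biologic initiation", with a two-encounter fallback. Table 1 grades all six outcomes against that baseline: any fall in exacerbations, hospitalizations or maintenance OCS, a 5% gain in FEV1, a 1-point gain in ACT, and any improvement in clinician impression. Section 3 words the FEV1 endpoint as "5% or greater improvement in FEV1 when compared to baseline FEV1". It does not say whether 5% is relative or in points, and section 4.1 abstracts lung function as % predicted.

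**Primary endpoint (section 1.1).** The binary form reads "Determine the cutoff value in chest wall muscle size/quality that optimally classifies patients that had and did not have any reduction in pre-treatment baseline exacerbation" (meaning its frequency). The continuous alternative is the relationship "between continuous chest wall muscle size/quality and continuous change in exacerbation frequency". Neither has a baseline term.

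**Secondary endpoints (section 1.1).** "Determine individual and combinations of body composition measures (phenotypes) associated with a 5% or greater improvement in FEV1", with parallel wording for OCS.

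**Models (section 6.3).** The stated method is "we will leverage the regularization technique in machine learning to select important variables and develop risk predictive models". The aim is "To incorporate high-dimensional morphomic parameters to better stratify patients in regard to their probability of complete response", and "elastic net regularization will be utilized to address the high dimensional nature of data derived with analytic morphomics"; random forest and gradient boosting are added. There is no list of candidate predictors, no forced-in covariate and no baseline-only reference model. (The target named there, complete response, differs from Table 1, which pools partial and complete responders; that is a separate matter.)

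**Baseline elsewhere.** Section 6.1 uses baseline characteristics for description and for comparing the two cohorts. Section 6.2 scales the CT measures for height and sex, and optionally age. Sections 5.1 and 5.2 require no prior exacerbation and no maintenance OCS use.

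**The concern.** The chance of passing a change threshold depends on where the patient starts. Someone with five exacerbations in the baseline year has more room for a decrease than someone with one, and someone with none cannot decrease at all. The same holds for hospitalizations and OCS dose. A CT measure that merely goes along with baseline severity will then separate responders from non-responders without saying anything about the drug.

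The protocol itself makes such a correlation plausible. Section 2.2 argues that air trapping and obesity risk in severe asthma should go with abnormal chest wall anatomy. Section 4.2 wants markers that predict response better than FeNO, eosinophils and IgE, but no planned analysis compares CT measures with anything the clinician already knows. Calgary is to be graded by the same labels, so external validation could confirm a proxy.

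**Working it through.** The documents give no exacerbation rate, effect size or marker correlation, so there is no planned figure to reproduce. From the documents come about 300 Michigan patients, about 15% expected non-response (0.15 × 300 = 45), and the Table 1 rules. The remaining inputs are assumptions. Any patient without a decrease is counted as a non-responder.

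**1. Zero baseline, by arithmetic.** Let p be the share with no baseline exacerbations (assumed 5 to 30%), with 15% non-response among the rest.
- Non-responders by construction = 300p; others = 0.15 × 300(1 − p).
- Share fixed by baseline = 300p / (300p + 45(1 − p)).
- No responder has baseline zero, so the indicator baseline = 0 has AUC = 0.5 + share/2.

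| p | Fixed by baseline | Other non-responders | Share fixed | AUC |
|---|---|---|---|---|
| 5% | 15 | 43 | 26% | 0.63 |
| 10% | 30 | 41 | 43% | 0.71 |
| 20% | 60 | 36 | 63% | 0.81 |
| 30% | 90 | 32 | 74% | 0.87 |

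Section 4.1 counts every hospitalization for asthma or breathing complaints as an exacerbation, so the zero share for hospitalizations cannot be smaller than for exacerbations.

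**2. Baseline above zero, by simulation.** Poisson counts, lognormal rates (mean 1 to 3 per year, log-rate SD 0.7), equal windows.
- No drug effect: the probability of any decrease is 0.23 to 0.44 at one baseline event and 0.63 to 0.84 at five.
- No effect or a uniform halving: baseline count alone has AUC 0.65 to 0.78 among patients with at least one event.
- A second set-up (gamma rates, mean 1 to 4, rate ratio 0.3 or 0.5 for everyone, 14-month follow-up annualised) gives 0.63 to 0.79 on the same restriction, and 0.86 to 0.99 over all patients.

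**3. False credit to a marker.** Second set-up with mean 2 or 3, shape 2, rate ratio 0.5, n = 300, 600 simulations, logistic test at 5%. The marker is correlated with the underlying rate but has no effect on treatment response.

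| Correlation | Flagged, no baseline term | Flagged, baseline > 0 and log baseline in model |
|---|---|---|
| 0 | 4–5% | 4–5% |
| 0.2 | 16–17% | 7–9% |
| 0.3 | 32–36% | about 18% |

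Two cautions apply. Part of the fall reflects fewer patients: 25% and 16% have baseline zero, leaving about 300 × 0.75 = 225 and 300 × 0.84 = 252. What remains also runs the other way: for a given baseline count, a higher underlying rate means more follow-up events and so less chance of a decrease. One year's count measures the rate with error, and adjustment cannot undo that.

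**4. FEV1.** True mean 62, SD 16, uniform gain of 4 points, within-patient SD 4 to 8. On the relative reading, 69–70% respond in the lowest baseline tertile against 36–43% in the highest, and low baseline has AUC 0.64 to 0.68. On the absolute 5-point reading the AUC is 0.58 to 0.64, from regression to the mean alone.

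**The case against.** **Section 6.3 is silent; it does not exclude.** A reader might infer that the models leave baseline out. The text lists no candidate predictors, and baseline data go into the same database, so analysts could enter them. That stands: the supportable statement is that no baseline term is specified. Silence is a weaker defence for the primary endpoint, because a single-marker cutoff has no place for baseline as written.

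**Strongest predictor, every endpoint.** A reader might also infer that baseline is the best predictor available and that the problem is equal across endpoints. Neither is shown. Baseline was not compared with eosinophils, FeNO or IgE. Only exacerbations and FEV1 were simulated, and clinician impression has no numeric baseline.

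**The assumed populations differ from the planned one.** The lognormal settings give non-response of about half (no effect) or a quarter (halving) among patients with a baseline event, against the expected 15%. That is fair. But the gamma setting closest to 15% (mean 4, shape 2, rate ratio 0.3: 15.9% non-response) has the highest baseline AUC of that set among patients with an event, 0.79, and 70% of its non-responders have baseline zero.

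**No correlation, no harm.** Correct, and the documents give no value. Section 2.2 makes a non-zero correlation the study's own premise but does not size it.

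**Adjust for age, sex and BMI as well?** Sex, and partly age, are handled by scaling. BMI is itself a body-composition surrogate (section 2.2), and forcing it in could absorb the signal under study.

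**Conclusion.** The point holds as a gap in specification with a practical consequence: followed as written, the plan yields results unadjusted for the value from which each label is computed. It is firmest for exacerbations, where baseline is a strong predictor even among patients with an event, and for the three endpoints where a zero baseline decides the label (26 to 74% of exacerbation non-responders if 5 to 30% start at zero). It is weaker for FEV1 and unquantified for ACT. The size of any false credit depends on two unknowns, the zero-baseline share and the marker's correlation with underlying severity; at zero correlation there is none. The documents do not support saying that baseline is excluded from section 6.3 or that it is the strongest predictor available. This should be changed before the outcome analyses are run.

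**What to change.** In sections 1.1 and 6.3:

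1. List the candidate predictors. For exacerbations, hospitalizations, OCS, FEV1 and ACT, enter the endpoint's own baseline value as an unpenalised term in the elastic net (penalty factor 0) and as a feature in the forest and boosting models.
2. Adjust the primary muscle analysis, cutoff and continuous form alike, for baseline exacerbations.
3. Analyse exacerbations, hospitalizations and OCS among patients with a baseline above zero, and report how many are set aside.
4. State whether the 5% FEV1 threshold is relative or in points of % predicted.
5. Report baseline-only and baseline-plus-morphomics models in Michigan and in Calgary, and rest any biomarker claim on the increment. Do not force in BMI.

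The data are already abstracted. The cost is wording, one extra model per endpoint, and a smaller analysis set for the count and dose endpoints, which matters with only about 45 expected non-responders in Michigan and 0.15 × 200 = 30 in Calgary. Because adjustment does not remove regression to the mean, describe an increment as better prediction of the label, not as proof that the marker alters response to the drug.
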